## 1.0 Purpose of the Study:

Chronic Obstructive Pulmonary Disease (COPD) is caused primarily by smoking and smoking cessation is the first-line treatment for slowing disease progression. Despite this, nearly 50% of COPD patients continue to smoke following diagnosis. Smokers with COPD report high rates of co-occurring conditions – nicotine dependence, depression, and anxiety – which serve as barriers to quitting. The proposed research will develop and pilot test a behavioral intervention designed to target the common psychological factors underlying these co-occurring conditions and foster smoking cessation among COPD patients. Specific aims are:

Aim 1: Refine behavioral treatment components. We will conduct a series of semi-structured qualitative interviews with COPD providers (pulmonologists, nurses, and respiratory therapists) that will elicit feedback on key elements of treatment design (components, methods, and milestones) and implementation (safety, tolerability, and acceptability) to guide treatment tailoring and foster engagement.

Aim 2: Develop a multi-component behavioral treatment to address psychological risk factors among COPD patients. We will conduct a component analysis using single case design experiments with 15 participants to a) examine the contribution of each treatment component to the behavioral target of smoking for affect regulation, and b) establish proof-of-concept on the clinical endpoint of initial cessation ( $\geq$ 24 hours abstinence). Hypothesis: Behavioral treatment components will produce a) clinically significant reductions in smoking for affect regulation ( $\geq$  30%), and b) achievement of initial cessation in  $\geq$  60% of participants.

Aim 3: Examine effects of psychological risk factor reduction on smoking outcome. Informed by Aim 2, we will conduct a pilot trial in which 62 participants are randomized to the multi-component behavioral treatment (9 weekly sessions) or self-guided treatment (mailing of printed self-help materials). Each participant will make a quit attempt at week 4. The primary outcome is number of days abstinent for 2 weeks post-quit (range = 0-14 days); secondary outcomes are smoking status at 3 months post-quit, COPD functioning, activity avoidance, and depression and anxiety symptoms. **Hypothesis**: Participants in the behavioral treatment vs. self-guided treatment will demonstrate a) greater number of abstinent days, and b) longer latency to smoke during the quit attempt.

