**Psychological factors are a promising treatment target.** Guided by recent systematic reviews and our preliminary, human laboratory-based work, we propose three core psychological factors that commonly underlie nicotine dependence, depression, and anxiety: distress intolerance (DI; inability to withstand distressing states), anxiety sensitivity (AS; fear of anxiety-related sensations), and anhedonia (Anh; diminished sense of pleasure or interest). As shown in Figure 1, we propose that each of these factors interacts with clinical symptoms specific to COPD to drive smoking persistence. First, DI promotes smoking for distress termination (i.e., during frequent bouts of acute withdrawal caused by high nicotine dependence) and results in exacerbation of COPD-specific symptoms. Second, AS promotes smoking for anxiety reduction especially when COPD patients experience distressing symptoms such as shortness of breath and leads to avoidance of activities that may increase these symptoms (i.e., physical exercise, engagement in pulmonary rehabilitation). Third, as activity avoidance cuts off contact with natural rewards in the environment, Anh promotes smoking for pleasure enhancement. Lastly, all three factors contribute to smoking persistence and perpetuate depression and anxiety symptoms, creating a cycle which serves as a powerful barrier to quit even among highly motivated individuals. In summary, these psychological factors index an individual's tendency to smoke to regulate affect (i.e., to enhance pleasure or reduce distress) in response to COPD-specific states and underlie smoking persistence among COPD patients.

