- 5. Lastly, participants will be provided with instructions on electronic diary completion. The study team member will provide each participant with written instructions on how to complete the REDCap questionnaires via smartphone, tablet, or computer. All participants will be provided with contact information for the research team should they have any questions about the electronic diary questionnaires.

Electronic Diary (ED) Assessment. ED assessments have demonstrated high compliance rates (>80%) among older adults, including those with chronic illness. Thus, we believe these methods are feasible for the current study. Participants will be prompted to complete nightly ED assessments via REDCap each evening (between 7:00 and 10:00 pm) during both baseline phase and treatment phase of the study. This will yield up to approximately 29 assessment timepoints for participants in the short baseline condition and 43 assessment timepoints for participants in the long baseline condition. In order to allow for the five-week treatment session

window described below, we will provide compensation for up to 36 assessment timepoints in the short baseline condition and up to 50 assessment timepoints in the long baseline condition.

Treatment Sessions. Each treatment component consists of 4 weekly in-person, individual sessions of 45-60 minutes each with a trained study therapist. We will attempt to schedule treatment sessions on the same day of each week, but will allow for a five-week window to complete all four sessions, to accommodate some rescheduling of sessions if needed. Session content is described in the Behavioral Treatment Components subsection below.

[figure not shown]
Target Quit Date. Each participant will set a target quit date on the day following the final treatment session. They will be instructed not to smoke starting at midnight (12:00 am) on their designated quit date.

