COPD-Related Measures			
Six-minute walk test	X		
Spirometry (FEV1)	X		
Charlson Comorbidity Index	X		
COPD Assessment Test	X		X
PROMIS- Dyspnea Task Avoidance	X		X
PROMIS- Dyspnea Emotional Response	X		X
Depression and Anxiety Measures			
PROMIS- Depression short form	X		X
PROMIS- Anxiety short form	X		X
Treatment-Related Measures			
Freiberg Mindfulness Inventory	X	X	X
Avoidance and Inflexibility Scale	X	X	X
Behavioral Activation for Depression			
Scale	X	X	X

Depression and Anxiety Symptoms. PROMIS short forms will be used to assess past-7 day depression and anxiety symptoms. 

Treatment Implementation. To assess treatment implementation, participants will complete process measures at each treatment session assessing skill acquisition specific to each module (i.e., Freiberg Mindfulness Inventory,  Avoidance and Inflexibility Scale,  and Behavioral Activation for Depression Scale,  respectively).

Behavioral Target. The behavioral target will be smoking for affect regulation, as measured by 13 items from the Smoking Motives Questionnaire-Revised (SMQ-R).  $^{33,60}$  Items are adapted from a measure of drinking motives and have been validated to assess coping motives across classes of substance use.  $^{32,60,61}$  SMQ-R items can be modified to assess within-subject, state-like motives for use via ecological momentary assessment  $^{62}$  and have demonstrated good internal consistency.  $^{63}$  Further, these items are sensitive to treatment-related change (i.e., reduced as a function of a brief behavioral intervention) $^{64,65}$  and specifically related to reductions in substance use and associated problems, above and beyond non-affective motives.  $^{64,65}$  Responses are scored from 0 (not at all) to 100 (extremely) and averaged to index the overall tendency to smoke for affect regulation. Threshold of clinically-significant change is set at  $\geq 30\%$ , as this change magnitude was associated with substance use outcomes in prior studies.  $^{64,65}$  Specific items which index smoking for distress termination (e.g., "To turn off negative thoughts about myself"), anxiety reduction (e.g., "Because it helped me when I was feeling nervous"), and pleasure enhancement motives (e.g., "To help me feel more positive about things in my life") will be examined separately in follow-up exploratory analyses.

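### Does Aim 3's heading, on the effect of reducing psychological risk factors, promise more than its outcomes and hypothesis can show?

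*Combined protocol and SAP*

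**What the plan says.** Section 1.0 opens Aim 3 with the words "Examine effects of psychological risk factor reduction on smoking outcome". The design beneath it randomises 62 participants to nine weekly sessions of the multi-component treatment or to "self-guided treatment (mailing of printed self-help materials"). The primary outcome is days abstinent in the two weeks after quitting (0 to 14), and "secondary outcomes are smoking status at 3 months post-quit, COPD functioning, activity avoidance, and depression and anxiety symptoms". The hypothesis begins "Participants in the behavioral treatment vs. self-guided treatment will demonstrate a) greater number of abstinent days" and adds a longer time to first smoking. Both parts compare the arms.

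Section 2.0 defines the risk factors: "we propose three core psychological factors that commonly underlie nicotine dependence, depression, and anxiety". These are distress intolerance, anxiety sensitivity and anhedonia. The same section links them with activity avoidance, depression and anxiety, "creating a cycle which serves as a powerful barrier to quit".

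The scales for the three factors (DTS, ASI-3, EROS) and the 13 SMQ-R items for smoking for affect regulation are described under Measures in Section 4.0, within Phase 2. The only analysis text, in Section 14.0, is also for Phase 2.

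**The concern.** The heading poses a question about mechanism: does lowering these factors change smoking? The listed outcomes contain neither the factors nor the smoking motive they are said to drive. Activity avoidance, depression and anxiety belong to the same model but are not the three factors, and Aim 3 states no link between their change and abstinence. Aim 2, by contrast, names its behavioural target and puts it in its hypothesis.

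The arms also differ in therapist contact (nine sessions against printed material) and apparently in counselling, since Procedures to Minimize Risk describes withdrawal as handled through either counselling or self-help materials. A difference in abstinent days could therefore arise with no change in any factor. The worry is that a positive pilot would be reported as evidence that reducing these factors helps people quit, when it shows only that the package outperformed mailed self-help.

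**Working it through.** The point depends on reading passages together. The plan gives no power, effect size or SD for the 62 participants, so there is no sample-size figure to reproduce. The sample total does check: 20 + 15 + 62 = 97.

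**1. Heading against operative text.**
- Heading: effect of risk factor reduction on smoking.
- Randomised contrast: whole treatment versus self-guided treatment.
- Primary outcome: abstinent days.
- Hypothesis: by arm, on abstinent days and latency.
- Overall Study Design (Section 4.0): a pilot randomised comparison of the behavioural intervention with minimally enhanced usual care.

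Four of the five describe a package comparison or fit one. Only the heading goes further, and nothing in the available text (sample, outcome, test or decision) depends on it.

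**2. Why the heading reads as it does.** Aim 3 is stated to build on Aim 2. In Phase 2, "Participants will be prompted to complete nightly ED assessments via REDCap each evening", giving about 29 or 43 timepoints. The diary's content is not spelled out, but "SMQ-R items can be modified to assess within-subject, state-like motives for use via ecological momentary assessment", Table 2 schedules the SMQ-R at baseline only, and Section 14.0 analyses change in the behavioural target over treatment. The diary is therefore the likely source. Section 14.0 admits to the Phase 3 manual only components that work on both milestones, one of which is the reduction in smoking for affect regulation. Its secondary rule, keeping all three components if every effect size is at least 0.5 and otherwise the best two, also ranks them on that target. Phase 3 thus tests a treatment chosen for acting on the pathway.

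**3. Is a Phase 3 measurement plan absent?** The available text points to one that is not shown.
- Tables run from 2 to 4 with no Table 3.
- Table 4 is titled by study phase but has only Phase 2 rows.
- Measures mentions a 3-month follow-up, whereas Phase 2 lasts about 35 or 50 days.
- Section 15.0 uses a withdrawal scale that is not in Table 2.
- Section 15.0 lists assessments on Days 0, 28, 42, 56 and 120. If week 4 is Day 28, then 28 + 14 = 42 closes the primary window and 120 − 28 = 92 days is three months after quitting. Day 56 = 8 × 7 is the ninth weekly session if the first falls on Day 0.

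These days fit Aim 3, so a Phase 3 schedule evidently exists. Whether it includes DTS, ASI-3, EROS or the SMQ-R cannot be told.

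**4. Does simulation add anything?** Assume 31 per arm (62 / 2), a normal outcome, a total effect of 0.7235 SD and a factor-to-outcome slope of 0.4. The arm comparison is then significant in 80.0%, 80.3% and 79.9% of 20,000 simulated trials when 0%, 50% and 100% of the effect runs through the factors. This is true by construction: 0.7235 SD is the effect that gives 80% power at 31 per arm, and a test of the total effect does not depend on its route. The 100% case needs a factor shift of 0.7235 / 0.4 = 1.81 SD. The run illustrates a general fact and does not measure a flaw in this trial.

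**5. What would extra mechanism outcomes buy?** The 95% half-width for a baseline-adjusted factor difference is t(0.975, 59) × √(1 − r²) × √(2/31). With assumed correlations r = 0.3, 0.5 and 0.7 and no dropout, this is 0.49, 0.44 and 0.36 SD, and the detectable differences at 80% power are 0.69, 0.63 and 0.52 SD. Only moderate-to-large shifts would show. The contrast would still mix technique with contact and counselling, so the literal heading would remain unproved.

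**The case for a change.** The strongest case for a change is that rewording costs nothing, the mismatch is plain on the page, and the heading concerns the trial's main inference. Phase 2 does not fill the gap. It has 15 participants, one module each and no control arm, and the three factor scales are scheduled only at baseline and about a week after the target quit date. Selecting components on the pathway in Phase 2 does not test mediation in Phase 3.

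Most of this stands. The heading is broader than what is listed, and a positive Phase 3 result would support only a package effect against mailed self-help. What does not follow is a defect in the plan. The by-arm hypothesis sits in the same paragraph as the heading and states what will be tested, so a reader who goes beyond it does so against the text. The call for added factor outcomes assumes a gap in Phase 3 measurement that the available text cannot establish.

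**Conclusion.** The concern is right about the wording and does not reach the plan. Aim 3's heading is shorthand for testing a treatment built to reduce these factors, while its design, primary outcome and hypothesis estimate the effect of the whole multi-component treatment versus self-guided treatment. Narrowing the heading would leave every procedure, estimate and test as it is. Adding mechanism outcomes to a 62-person pilot is a matter of preference: it may already be planned, it would detect only differences of about 0.5 to 0.7 SD (31 per arm, no dropout, assumed correlations of 0.3 to 0.7), and it would not isolate technique from contact.

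This rests on two readings: that the by-arm hypothesis governs over the heading, and that a Phase 3 schedule exists outside the available text. If that schedule omits the factor scales, the conclusion about the heading is unchanged, since the randomised comparison would still answer the hypothesis as written. Analysts need only report the result as a treatment effect.

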# 2.0 Background / Literature Review / Rationale for the study:

Chronic Obstructive Pulmonary Disease (COPD) is the third leading cause of death in the United States, responsible for 135,000 deaths each year. COPD is caused primarily by smoking and approximately 47% of those with COPD are current smokers.

**Smoking cessation is imperative for COPD patients.** Quitting smoking is the most effective and cost-effective therapy for COPD. As compared to smokers in the general population, COPD patients are equally

motivated to quit and attempt to quit at equal rates, but are less responsive to smoking cessation treatment, with only 12% abstinent at 12 months. COPD patients commonly have cooccurring conditions – high nicotine dependence, depression, and anxiety

Figure 1. Conceptual model of psychological factors and smoking persistence among COPD patients Psychological Distress Intolerance **Anxiety Sensitivity** Anhedonia Factors Affect Regulation Distress Anxiety Pleasure Smoking Motives Termination Reduction Enhancement High COPD-Specific Nicotine Symptoms (i.e., Smoking Persistence Activity Avoidance Clinical Dependence Shortness of Breath) Presentation Depression Anxiety

– that maintain smoking for negative reinforcement (i.e., reduction of withdrawal-related distress).  To improve upon stagnant quit rates among COPD patients, novel, targeted treatment strategies are needed.

**Psychological factors are a promising treatment target.** Guided by recent systematic reviews and our preliminary, human laboratory-based work, we propose three core psychological factors that commonly underlie nicotine dependence, depression, and anxiety: distress intolerance (DI; inability to withstand distressing states), anxiety sensitivity (AS; fear of anxiety-related sensations), and anhedonia (Anh; diminished sense of pleasure or interest). As shown in Figure 1, we propose that each of these factors interacts with clinical symptoms specific to COPD to drive smoking persistence. First, DI promotes smoking for distress termination (i.e., during frequent bouts of acute withdrawal caused by high nicotine dependence) and results in exacerbation of COPD-specific symptoms. Second, AS promotes smoking for anxiety reduction especially when COPD patients experience distressing symptoms such as shortness of breath and leads to avoidance of activities that may increase these symptoms (i.e., physical exercise, engagement in pulmonary rehabilitation). Third, as activity avoidance cuts off contact with natural rewards in the environment, Anh promotes smoking for pleasure enhancement. Lastly, all three factors contribute to smoking persistence and perpetuate depression and anxiety symptoms, creating a cycle which serves as a powerful barrier to quit even among highly motivated individuals. In summary, these psychological factors index an individual's tendency to smoke to regulate affect (i.e., to enhance pleasure or reduce distress) in response to COPD-specific states and underlie smoking persistence among COPD patients.

Behavioral treatment can address psychological factors and promote cessation. Cognitive-behavioral treatment strategies have been shown to effectively reduce these psychological factors among a general population of cigarette smokers as well as individuals with chronic illness, elevated depressive symptoms, and substance use disorders. These treatment strategies reduce reliance on smoking for affect regulation and improve cessation rates. Ours will be the first study to adapt a behavioral treatment to specifically target these psychological factors among COPD patients. Effectively addressing psychological conditions is also shown to increase COPD patients' exercise tolerance, engagement in pulmonary rehabilitation, and quality of life. Thus, this intervention has potential to obviate a large number of health burdens among COPD patients.

### 3.0 Inclusion and exclusion criteria:

For COPD patients in Phases 2-3, study eligibility will be determined as follows: Inclusion criteria: Eligible participants will be males and females who are 1) diagnosed with COPD (as documented in electronic health record [EHR]), 2) daily cigarette smokers ( $\geq$  5 cigarettes per day over past 30 days), 3) intend to quit smoking within the next 60 days, 4) report at least moderate level of smoking for affective regulation (SMQ-R coping subscale score  $\geq$ 30), 5) have access to a smartphone, tablet, or computer, and 6) are able to communicate fluently in English. Exclusion criteria: We will exclude based on presence of any concurrent medical or psychiatric condition which would preclude ability to provide informed consent or perform study procedures (e.g., moderate to severe dementia and/or severe, uncontrolled schizophrenia), as determined by the treating physician or study PI.

We will not include adults unable to consent, pregnant women, prisoners, or individuals under the age of 18. Socioeconomically disadvantaged persons will be included in this study, but not targeted for recruitment. It is possible that Rush University employees or students may choose to participate. However, status of participation in the study will be independent of the participant's work or school activities.

### 4.0 Procedures Involved:

[figure not shown]
### **Overall Study Design**

The project includes a total of three phases that will each recruit an independent sample of participants, as shown in Table 1 below. A total of 97 participants will be recruited for the current study. First, Phase 1 will

involve qualitative interviews with COPD healthcare providers (N=20). In Phase 2, we will conduct a series of single case design experiments in which COPD patients (N=15) will complete behavioral treatment components before an attempt to quit smoking. Lastly, Phase 3 consists of a pilot randomized, controlled trial comparing the behavioral intervention to minimally-enhanced usual care (N=62).

### **Phase 2: Single Case Design Experiments**

**Procedure.** Single case design experiments offer a rigorous and methodologically-sound procedure to test within-subject change across conditions (i.e., baseline to active treatment) in a replication context to efficiently evaluate interventions. Specifically, we will conduct a component analysis using a series

of 15 single-case design experiments. As shown in Figure 2, a non-concurrent multiple baseline design (1-3 weeks in length) will be used across participants to observe if change in the behavioral target occurs when, and only when, a treatment module is introduced, thus controlling for the effects of extraneous factors. The overall goal of Phase 2 is to examine whether each treatment component in isolation follows the hypothesized pathway in Figure 3.

Length of Study Participation. As shown in Figure 2, participants who are randomized to the short baseline condition will be enrolled in the study for approximately 35 days; participants randomized to the long baseline condition will be in the study for approximately 50 days.

Pre-Screening and Baseline Session. Participants will complete an initial pre-screening questionnaire administered by telephone or computer, using surveys developed in REDCap software, version 6. Eligible participants will be scheduled for an in-person baseline session approximately 1.5 hours in length. The following procedures will be completed at the baseline session:

- 1. Informed consent/HIPAA forms will be reviewed with participants, during which they will hear a description of all study procedures, risks, benefits, and information about the study medication. Participants' questions will be answered. Following this discussion, the combined informed consent and HIPAA form will be completed.
- 2. A carbon monoxide (CO) breath assessment will be used to measure recent tobacco exposure. The handheld device uses a disposable mouthpiece, reports CO in parts per million (ppm), and takes about three minutes to administer.
- 3. Participants will complete questionnaire measures of smoking-related variables, psychological factors, and COPD-related variables, as described below.
- 4. Following a randomization scheme programmed in REDCap, participants will be randomized to baseline length (long or short) and treatment condition (Mindfulness, Interoceptive Exposure, or Behavioral Activation, described below).
- 5. Lastly, participants will be provided with instructions on electronic diary completion. The study team member will provide each participant with written instructions on how to complete the REDCap questionnaires via smartphone, tablet, or computer. All participants will be provided with contact information for the research team should they have any questions about the electronic diary questionnaires.

Electronic Diary (ED) Assessment. ED assessments have demonstrated high compliance rates (>80%) among older adults, including those with chronic illness. Thus, we believe these methods are feasible for the current study. Participants will be prompted to complete nightly ED assessments via REDCap each evening (between 7:00 and 10:00 pm) during both baseline phase and treatment phase of the study. This will yield up to approximately 29 assessment timepoints for participants in the short baseline condition and 43 assessment timepoints for participants in the long baseline condition. In order to allow for the five-week treatment session

window described below, we will provide compensation for up to 36 assessment timepoints in the short baseline condition and up to 50 assessment timepoints in the long baseline condition.

Treatment Sessions. Each treatment component consists of 4 weekly in-person, individual sessions of 45-60 minutes each with a trained study therapist. We will attempt to schedule treatment sessions on the same day of each week, but will allow for a five-week window to complete all four sessions, to accommodate some rescheduling of sessions if needed. Session content is described in the Behavioral Treatment Components subsection below.

[figure not shown]
Target Quit Date. Each participant will set a target quit date on the day following the final treatment session. They will be instructed not to smoke starting at midnight (12:00 am) on their designated quit date.

Remote CO Assessment. At the final treatment session, participants will be provided with a carbon monoxide (CO) monitor and trained to submit a breath CO sample via REDCap at 24-hours post-QA (i.e., upon waking on Day 30 for the short baseline condition or Day 44 for the long baseline condition). This procedure will be used to conduct remote bioverification of smoking status. Developed by [name], a study collaborator at the University of Florida, 38-43 this method has demonstrated feasibility among a variety of populations, including older adults. We will provide each participant with written instructions and contact information for the research team should they have any questions about the CO monitor.

End-of-Treatment Session. Participants will return for an end-of-treatment (EOT) study assessment approximately one week following their target quit date. At this assessment, participants will complete a final set of questionnaire measures on smoking-related variables, treatment implementation variables, and the behavioral target of smoking for affect regulation, described below. Participants will also return the CO monitor device and receive compensation for all completed ED assessments.

Behavioral Treatment Components. Treatment components are cognitive-behavioral strategies

adapted from the Unified Protocol (UP) for the Transdiagnostic Treatment of Emotional Disorders. For the current study, we will evaluate only the three modules that have been shown to reduce reliance on smoking for affect regulation before a QA

and provide skills to cope with acute nicotine withdrawal after quitting: Mindfulness, Interoceptive Exposure, and Behavioral Activation (described below).

Behavioral counseling strategies for smoking cessation, drawn from current US Public Health Service guidelines, are incorporated in each treatment module. All participants will be provided with the American Lung Association Freedom from Smoking guide to aid in their quit attempt.

Component 1: Mindfulness. This module introduces mindfulness training skills, with the goal of cultivating nonjudgmental, present-focused experience of emotions, thoughts, and physical sensations related to cigarette smoking. By progressing though a series of experiential exercises (e.g., awareness of the breath, anchoring in the present), this module seeks to reduce maladaptive attempts to control negative emotions and facilitate tolerance of the physical and emotional symptoms of nicotine withdrawal.

Component 2: Interoceptive Exposure (Practice Quitting). This module introduces interoceptive exposure, a technique in which participants purposefully and systematically complete exercises to evoke physical sensations typically associated with anxiety and distress, in order to reduce fear and avoidance of these sensations. Interoceptive exercises will focus on a gradual exposure to nicotine withdrawal symptoms, through a series of 'practice quit attempts' (i.e., brief periods of smoking abstinence without intention to permanently quit).

Component 3: Behavioral Activation (Countering Emotional Behaviors). Lastly, this module introduces behavioral activation, which seeks to increase positive emotions by systematically introducing greater

engagement with natural rewards. Treatment sessions focus on the identification of avoidance strategies, including cigarette smoking as a coping strategy for negative emotions. The goal of this treatment module is to replace smoking with adaptive coping strategies to facilitate contact with and enjoyment of reinforcing activities that are incompatible with smoking.

Treatment Fidelity. All treatment sessions will be delivered by trained study counselors, supervised by the PI, a licensed clinical psychologist. [name] has extensive experience in cognitive-behavioral therapy for mood and anxiety disorders, as well as behavioral counseling for smoking cessation. She obtained specialized training in delivery of the proposed intervention at the Unified Protocol Institute at Boston University in October, 2017. Sessions will be audio recorded, with 20% of sessions reviewed by an independent evaluator using standardized fidelity ratings for each UP module.

